After determination of eligibility, participants will have a one-day CTRC admission for baseline laboratory studies, IVGTT, and body composition assessment (Study Visit 1) following an overnight fast. Upon arrival they will have an IV placed for blood draws and injections. Fasting blood glucose and insulin will be drawn at this time. Sex steroids and inflammatory markers will also be drawn at this time. (After the blood draw, they will undergo a frequently sampled IVGTT (specific methods for above described after Specific Aim 2). Up to 10 obese subjects will participate in the arm, as pilot subjects, who **are not** part of the treatment arm (i.e. they will not be taking a placebo).

In the afternoon of the Study Visit 1, a dual-energy x-ray absorptiometry (DEXA) scan will be performed to determine body composition. In a subset of participants (13 per group), soleus muscle nuclear magnetic resonance (NMR) and abdominal fast magnetic resonance imaging (MRI) sequence will also be performed to measure body fat distribution in terms of IMCL, liver fat content and visceral adipose content.

The next study visit (Study Visit 2) will occur when the participant has reached Tanner stage IV, approximately one year after the baseline visit. At this time the baseline laboratory draw, imaging studies and IVGTT will be repeated. For those subjects randomized to the MRI, it will not be repeated at this visit.

The next study visit (Study Visit 3) will occur when the participant has reached Tanner stage V, approximately one year after Study Visit 2. At this time the baseline laboratory draw, imaging studies and IVGTT will be repeated. This is the last long visit for the lean subjects. The obese subjects will stop taking the study medication at this time point.

The next study visit (Study Visit 4) will occur 6 months after the obese participants have reached Tanner stage V. At this time the baseline laboratory draw, imaging studies and IVGTT will be repeated. This is the last long visit for the obese subjects. For those subjects randomized to the MRI, it will not be repeated at this visit.

Between the visits, participants will be asked to come in every 6 months for anthropometric measurements and Tanner staging. Obese participants in the treatment arm (randomized to either Metformin or placebo) will also be asked to come in quarterly for pill counts to measure medication compliance and to receive a refill on their medication.

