β -cell function will be preserved. This would make puberty a potential treatment period to target prevention of T2DM.

DESIGN

Participants:

1. 104 Obese participants:
 - a.) BMI \geq 95th percentile
 - b.) Tanner stage II – III at baseline
 - c.) Age \geq 9 years
 - d.) Absence of impaired glucose tolerance (IGT), impaired fasting glucose (IFG) or T2DM, as determined by oral glucose tolerance test (OGTT)

Exclusion criteria:

See Specific Aim 1

Approach:

All obese subjects who are recruited will be randomized after Study Visit 1 to receive metformin or placebo. The 52 participants randomized to the placebo group will then also serve as the obese subjects for the longitudinal observational studies of Specific Aim 1 (Please see Fig 2 for further clarification). In other words, 52 obese participants will be included in both Specific Aims 1 and 2, in order to minimize the total number of participants needed. Randomization will be stratified by: 1) Family history in a first degree relative with T2DM or no family history and 2) BMI between the 95th and 99th percentile or BMI greater than the 99th percentile. The extended release metformin will be started at 500 mg daily for one week and then increased by 500 mg a week until the target dose of 2000 mg a day is attained. The extended release preparation allows patients to take the medication once a day to promote improved adherence and is better tolerated. All obese participants will receive standard lifestyle counseling, focusing primarily on dietary improvements and increased physical activity. The total treatment period will be two years to include, on average, the most resistant stages of puberty. In order to monitor metformin compliance closely, the participants will come in for monthly pill-counts. In addition, each participant will be provided with a pill dispenser and a calendar to record each dose that is taken to assist with and track compliance. Furthermore, parents will be encouraged to remind the participant to take his/her medication. Participants will be given a point each time they bring in their pill bottle, whether or not they have been compliant, and will be eligible for an extra gift card for every 6 points they obtain. Our group has extensive experience in maintaining metformin compliance in this population (52). Tanner staging, anthropometric measurements and lifestyle counseling will also be performed at quarterly visits.

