Sample size calculation: A recruitment goal of 52 participants per group has been set (normal weight controls, obese controls, obese on metformin—a total of 156 participants). Assuming a 30% drop-out rate, this will give a final sample size of 30 per group. Power was run in PASS (NCSS Software; Kayesville, UT) and was calculated using a one-way ANOVA with a two-sided significance level of 0.05. Variability of the estimates was based on data available in an article by Buchanan et al. (57) in which IVGTT insulin sensitivity was measured in high-risk Hispanic women at baseline and 3 months for a placebo (n=109) and a troglitazone group (n=108). The 3-month change was -0.17 and 1.16 min^{-1} per $\mu\text{U}/\text{ml} \times 10^{-4}$, for the placebo and treatment groups, respectively. Assuming a correlation of 0.5, the estimated overall standard deviation of the 3-month change for both the placebo and treatment groups was 1.85 min^{-1} per $\mu\text{U}/\text{ml} \times 10^{-4}$. For this study, we assume similar variability and expect the 2-year change for the obese control and metformin groups to also be similar to those seen in the Buchanan et al. groups. The 2-year insulin sensitivity change in normal controls is expected to be similar to the change seen in Ball et al. (11) for 46 white adolescents from Tanner II / Tanner III to Tanner V, which was 1.6 min^{-1} per $\mu\text{U}/\text{ml} \times 10^{-4}$. Therefore, with a standard deviation of 1.85 and expected 2-year changes of 1.16, -0.17 and 1.6 for the metformin, obese control and normal control groups, respectively, a sample size of 30 per group achieves 93% power to detect an overall difference between the groups.

Statistical analysis: All analyses will assume a two-sided test of hypothesis with an overall significance level of 0.05 and will be performed in either SAS v9.1.3 or above (SAS Institute, Inc., Cary NC) or Splus v7.0 or above (Insightful Corp, Seattle WA).

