Simple descriptive statistics will be calculated for all variables (mean, median, standard deviation, minimum and maximum values for continuous variables; number and percentage of subjects for categorical variables). Linear regression will be used to compare 2-year change in insulin sensitivity, insulin secretion, and DI between groups for Specific Aims 1 and 2 (normal controls vs. obese controls and obese treated vs. obese controls). Potential confounders such as sex, 2-year change in percent body fat and 2-year change in BMI will be included in each model. In order to determine if the benefit of treatment persists beyond stopping treatment, the above analysis will be repeated on the change from baseline to 6 months post-treatment for the obese treated and obese control groups only. The mean change in each outcome from treatment stoppage to 6 months post treatment will also be calculated with 95% confidence intervals (CI) in order to assess maintenance of the level of each outcome. Although we are not powered for equivalence (to test the hypothesis that the 6-month change is equal to zero), the precision of the estimate and whether the difference is *clinically* significant will be evident from the 95% CI. A CTRC biostatistician will be available to consult on all matters of statistics.

Potential Difficulties and Limitations/Alternatives

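### The Aim 2 metformin versus placebo model names neither the baseline outcome nor the randomisation strata as covariates: likely lost precision, not bias

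*Combined protocol and SAP*

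**What the plan says.** All references are to the combined protocol and SAP, section D.

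- **Model.** Statistical analysis: "Linear regression will be used to compare 2-year change in insulin sensitivity, insulin secretion, and DI between groups". The same model serves the non-randomised Aim 1 comparison (normal weight versus obese controls) and the randomised Aim 2 comparison (obese treated versus obese controls).
- **Covariates.** "Potential confounders such as sex, 2-year change in percent body fat and 2-year change in BMI will be included in each model". The list is worded as examples, so it is open. The only named terms are sex and two changes that occur after randomisation.
- **After treatment stops.** "the above analysis will be repeated on the change from baseline to 6 months post-treatment", so the same covariate set carries over.
- **Baseline is available before randomisation.** The Specific Aim 1 Approach places the first IVGTT at Study Visit 1. The Specific Aim 2 Approach then says: "All obese subjects who are recruited will be randomized after Study Visit 1 to receive metformin or placebo".
- **Strata.** "Randomization will be stratified by: 1) Family history in a first degree relative with T2DM or no family history"; the second factor is "BMI between the 95th and 99th percentile or BMI greater than the 99th percentile".
- **Planning values.** Sample size calculation: "Assuming a correlation of 0.5, the estimated overall standard deviation of the 3-month change for both the placebo and treatment groups was 1.85".

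No other section adds the baseline outcome or the strata to the model. The 2-year change in BMI is measured after randomisation and does not stand in for the baseline BMI band.

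**The concern.** Metformin versus placebo is the only randomised comparison in the study, and the plan reports no power for it; the stated 93% belongs to the three-group test. In a randomised comparison, a change score and a baseline-adjusted analysis estimate the same effect, and in large samples the change score cannot be the more efficient of the two. Leaving baseline out keeps in the error term the noise from chance baseline imbalance and regression to the mean.

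Naming the stratification factors matches the analysis to the randomisation. No precision gain is claimed for them, because the documents do not say how well they predict the outcome. An open covariate list can also be completed after the data are seen; naming the baseline terms in advance closes that route.

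**Working it through.** **Inputs (Sample size calculation).** SD of change 1.85; assumed correlation r = 0.5; expected changes 1.16 (metformin), −0.17 (obese control) and 1.6 (normal control); two-sided 5% level; 30 evaluable per group. The Aim 2 difference is 1.16 − (−0.17) = 1.33. Because 52 recruited with 30% drop-out leaves 52 × 0.70 = 36.4 rather than 30, both 30 and 36 per arm are shown.

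**1. The plan's own figure.** One-way ANOVA, noncentrality n·Σ(mᵢ − m̄)²/SD² = 30 × 1.698/3.4225 = 14.89 on 2 and 87 df. Power is 93.45%, so the stated 93% reproduces.

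**2. The Aim 2 contrast as an unadjusted change score.** SE = 1.85·√(2/30) = 0.478. Noncentral t power is 78.2% at 30 per arm and 85.3% at 36.

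**3. Adding baseline.** With equal variance s² at both visits, Var(change) = 2s²(1 − r) and the ANCOVA residual variance is s²(1 − r²). The ratio is (1 + r)/2 = 0.75 at r = 0.5, a 25% cut. Residual SD = 1.85·√0.75 = 1.602; SE = 1.602·√(2/30) = 0.414.

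| Per arm | Change score, unadjusted | With baseline | Unadjusted n per arm for similar power |
|---|---|---|---|
| 30 | 78.2% | 88.5% | 40 (88.8%) |
| 36 | 85.3% | 93.5% | 48 (93.6%) |

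Keeping equal variances and SD of change 1.85, power with baseline at 30 per arm is 92.4% for r = 0.3 and 84.3% for r = 0.7.

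**4. Unequal variances.** Let k = follow-up SD / baseline SD. Variance cut = 1 − k²(1 − r²)/(1 + k² − 2rk). The documents give no visit-specific SDs, so the ranges of k and r are assumptions. Percent cut:

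| r | k = 0.8 | 1.0 | 1.25 | 1.5 | 2.0 |
|---|---|---|---|---|---|
| 0.3 | 49.8 | 35.0 | 21.6 | 12.9 | 4.2 |
| 0.5 | 42.9 | 25.0 | 10.7 | 3.6 | 0.0 |
| 0.7 | 37.2 | 15.0 | 1.9 | 0.2 | 7.3 |
| 0.9 | 39.2 | 5.0 | 5.0 | 22.3 | 45.7 |

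The cut vanishes where rk = 1, because the slope on baseline is then 1 and the change score is already the efficient analysis.

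**5. Small-sample cost.** Simulated power (20,000 trials per cell; SD of change 1.85; two strata balanced across arms; strata and sex given no effect):

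| n per arm, r, k | Change score | Baseline | Baseline + strata + sex |
|---|---|---|---|
| 30, 0.5, 1.0 | 77.7% | 87.8% | 87.1% |
| 30, 0.3, 0.8 | 78.8% | 97.0% | 96.7% |
| 30, 0.5, 2.0 (worst) | 77.9% | 77.1% | 76.3% |
| 36, 0.5, 1.0 | 85.2% | 93.3% | 92.9% |
| 36, 0.3, 0.8 | 84.8% | 98.7% | 98.6% |
| 36, 0.7, 1.5 (worst) | 85.1% | 84.4% | 83.8% |

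The worst losses are 1.6 points at 30 per arm and 1.3 at 36. With strata left unbalanced (10,000 trials per cell) they are 2.8 and 1.9.

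**6. Bias.** In a separate simulation of 60 patients randomised within four strata (4,000 trials per scenario), a true effect of 1.33 gave mean estimates of 1.32 to 1.34 with and without adjustment. Type I error was 4.8% to 5.5% for every model. The empirical SE fell from about 0.48 to about 0.42.

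**The case against.** The strongest reply is that nothing here is an error. The change-score comparison is valid, and the open list would let baseline and strata in under the present wording. Further, the rise from 78.2% to 88.5% is not measured against the planned model, which also contains sex and the two post-baseline changes. If those terms happened to explain 25% of the variance of change (an illustration; the documents give no figure), the planned model would already have about 88% nominal power at 30 per arm. The 25% cut itself follows from a correlation assumed for a 3-month change in adult women and from equal variances, which the documents do not state. In the grid, 7 of 20 cells give a cut of 5% or less, although another 7 give 25% or more. No gain is shown for the strata, insulin secretion or DI.

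All of this stands as a limit on the size of the gain. It does not make the stated model equivalent to a baseline-adjusted one: a list that merely permits baseline does not commit to it. The efficiency result is a large-sample one, but the simulated losses at 30 to 36 per arm stay within 3 points, against gains of up to about 18.

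**Conclusion.** The point holds as an improvement in precision of uncertain size. The planned Aim 2 comparison is under-specified; this omission does not bias it. On the plan's SD and correlation, with equal variances, baseline adjustment is worth about 10 power points at 30 per arm (78.2% to 88.5%) and about 8 at 36 (85.3% to 93.5%), relative to an unadjusted change score. Over the assumed grid of r from 0.3 to 0.9 and k from 0.8 to 2.0, the variance cut is 0% to 50%. Power with baseline, balanced strata and sex is then 76% to 97% at 30 per arm and 84% to 99% at 36.

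These figures apply to insulin sensitivity only, since no SD is given for insulin secretion or DI, and to a model without the 2-year changes in BMI and percent body fat. The gain over the planned model cannot be computed from the documents. The statement that there is no bias concerns this omission in the randomised comparison alone. It does not extend to Aim 1 or to adjustment for post-randomisation changes. It could also fail if drop-out depends on baseline insulin sensitivity.

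**What to change.** For Aim 2, prespecify ANCOVA of each end-of-treatment outcome and each 6-month post-treatment outcome on treatment, the baseline value of the same outcome, family history of T2DM, baseline BMI band and sex. Baseline Tanner stage (II or III) may be added: the Background and the Specific Aim 1 Rationale describe insulin sensitivity as lowest at stage III.

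State separately whether the 2-year changes in BMI and percent body fat stay in the model. Keeping them changes what the treatment effect means, and the power figures here then do not apply.

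For Aim 1, keep the change score without baseline adjustment. Those groups are not randomised, and the Specific Aim 1 Rationale expects obese adolescents to enter puberty more insulin resistant, so conditioning on baseline would ask a different question.

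Adding baseline and the two strata changes only the analysis text and uses data already collected. It takes 3 degrees of freedom beyond the planned sex term. At r = 0.5 with equal variances and balanced strata, the strata and sex together cost under 1 power point relative to baseline alone. The decision on the post-randomisation changes is a further one that this wording does not settle.

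### The change-score regression has no missing-data method: anyone without the end-of-puberty IVGTT drops out, and the Tanner IV IVGTT enters no group comparison, so contrasts can be biased if dropout differs by group

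*Combined protocol and SAP*

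**What the plan says.** Statistical analysis: "Linear regression will be used to compare 2-year change in insulin sensitivity, insulin secretion, and DI between groups". The same regression is repeated for the change from baseline to six months post-treatment in the two obese groups, and a mean change from treatment stop is given with a confidence interval. Each model also carries sex and the 2-year changes in percent body fat and in BMI. Missing data, analysis population and sensitivity analyses are not mentioned.

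Sample size calculation: "A recruitment goal of 52 participants per group has been set", then "Assuming a 30% drop-out rate, this will give a final sample size of 30 per group".

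Visit schedule, in two forms:
- Specific Aim 1, Approach: "The next study visit (Study Visit 2) will occur when the participant has reached Tanner stage IV, approximately one year after the baseline visit", with an IVGTT at that visit, another at Tanner V and, for obese participants, one six months later. Both visit tables mark an IVGTT at Study Visit 2.
- Section A lists IVGTTs only in early puberty, at the end of puberty and, for the treatment arm, six months later. The Specific Aim 2 Approach makes Study Visit 2 the end of treatment and Study Visit 3 the six-month follow-up, with no Tanner IV IVGTT.

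Potential Difficulties and Limitations acknowledges attrition, but answers it with retention measures only.

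**The concern.** A regression on one change score uses only participants who have both ends of the change. With no other method stated, someone who leaves early is lost to the comparison even if a baseline and a Tanner IV IVGTT were done. The two change covariates reinforce this, because they too need end-of-study measurements.

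Two things are at stake. The first is validity. If participants who have responded poorly by Tanner IV leave more often in one group than in another, the completers' contrast is shifted. The second is precision: valid IVGTT data from 16 to 22 of every 52 participants would go unused in the group comparison, in a study of children for whom the plan itself wants to limit invasive procedures.

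**Working it through.** **Inputs from the sample-size section.** 52 recruited per group; 30% dropout; final n 30; two-sided alpha 0.05; "with a standard deviation of 1.85 and expected 2-year changes of 1.16, -0.17 and 1.6 for the metformin, obese control and normal control groups". The metformin minus obese control difference is 1.16 − (−0.17) = 1.33. The plan's SD rests on "Assuming a correlation of 0.5, the estimated overall standard deviation of the 3-month change". With ρ = 0.5 and equal visit SDs, the SD of a change is σ√(2(1 − ρ)) = σ, so σ = 1.85 and σ² = 3.4225.

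**Assumed, not in the documents.** The correlation r of Tanner IV with each adjacent visit is 0.5–0.7. Of the 16 dropouts per group, 8–16 have a Tanner IV IVGTT. The plan's ρ = 0.5, used there for a 3-month change, is carried over to two years.

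**1. The plan's own figures.**
- Power: "a sample size of 30 per group achieves 93% power to detect an overall difference between the groups". The mean of the three changes is 0.863, and the noncentrality is 30 × Σ(μᵢ − 0.863)²/3.4225 = 14.9 on 2 and 87 df. Power is 93.5%, so the stated figure reproduces.
- Dropout: 52 × 0.70 = 36.4, not 30. Thirty of 52 is a 42.3% loss. The planned loss is therefore about 16 per group by the stated rate, or 22 by the stated final n.
- Metformin vs obese control by t-test: power 78% at 30 per group, 85% at 36, and 95% if all 52 were observed.

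**2. Precision, 36 completers of 52.**
- Completers' change score: 2σ²/36 = 6.845/36 = 0.190.
- Repeated measures, baseline data only: 2σ²[(1 − ρ²)/36 + (1 − ρ)²/52] = 6.845 × (0.75/36 + 0.25/52) = 0.176, about 8% lower.
- The same with a common baseline mean, for the two randomised arms: the last term cancels, giving 6.845 × 0.75/36 = 0.143, 25% lower. Baseline adjustment of the completers alone gives the same 25%.
- With n₂ participants also seen at Tanner IV: 2σ²[(1 − R²)/36 + b²(1 − r²)/n₂ + (1 − ρ)²/52], where b = r(1 − ρ)/(1 − r²) and R² comes from regressing Tanner V on the two earlier visits. The last term again drops with a common baseline.

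| r | n₂ | b | R² | Plain | Common baseline |
|---|---|---|---|---|---|
| 0.5 | 44 | 0.333 | 0.333 | 0.173 (−9%) | 0.140 (−27%) |
| 0.7 | 52 | 0.686 | 0.490 | 0.161 (−15%) | 0.129 (−32%) |

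The Tanner IV data therefore add about 2 to 7 percentage points beyond the baseline data.

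In simulation with random dropout, power for metformin vs obese control is about 85–87% (completers) against 87–91% (plain repeated measures) at 30% loss, and 78–81% against 83–87% at 42% loss.

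**3. Bias.** Dropout is simulated as logistic on the baseline-to-Tanner IV change, 30% overall, with all losses after Tanner IV. The ranges are for r = 0.5–0.7.

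| Lost in worst vs best quarter of change | Bias in completers' mean change |
|---|---|
| 38% vs 22% | +0.08 to +0.11 |
| 46% vs 16% | +0.16 to +0.20 |
| 56% vs 10% | +0.24 to +0.30 |

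If this happens in one arm only, it passes straight into the contrast: 0.08/1.33 = 6% up to 0.30/1.33 = 23%.

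A separate simulation used log-odds of 1 per 1.85 units of change, with half or all of the losses after Tanner IV and 30% loss. The completers' contrast was 1.08–1.19 when worsening placebo participants left, and 1.48–1.58 when metformin non-responders left. The repeated-measures estimate stayed at 1.32–1.34. When dropout was random, or equally selective with the same overall loss in both arms, both methods gave about 1.33.

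**The case against.** - **The Tanner IV IVGTT may not exist.** Section A and the Specific Aim 2 Approach do not include it. This stands: the schedule has to be reconciled first, and only part of the gain depends on that visit.
- **The endpoint is deliberate.** The plan explains that insulin sensitivity at Tanner IV may not yet differ from earlier stages, so Tanner V is the right time to compare. This stands too, but the proposed model keeps Tanner V as the target and uses Tanner IV only to inform missing Tanner V values. The planned descriptive statistics would also cover Tanner IV, so the data are not wholly unused; they are absent from every group comparison.
- **Differential dropout is not shown.** The group's earlier metformin trial found no significant attrition difference, and the plan says adverse effects did not cause significant attrition. That trial lasted six months, against two years or more here, and equal rates do not establish equal reasons for leaving. Still, these statements are the only attrition evidence in the documents, and they do not show a bias.
- **Early leavers are not rescued.** Someone who leaves before about one year has no Tanner IV IVGTT. This is true; only the baseline is recovered for them.

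A reader might infer that the plan prescribes a completers-only analysis, that the metformin contrast will be biased, or that the 9–32% variance reduction comes from the Tanner IV test. The documents do not support these. The first is an inference from silence about missing data. The second needs outcome-related dropout that differs by group. The third is contradicted by the calculation, in which baseline data alone give 8% or 25%.

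**Conclusion.** The point holds as a gap in the analysis plan that is cheap to close. The single stated between-group method leaves out participants without the end visit, the plan expects to lose 30–42% of each group, and nothing says how that loss is handled. Bias is possible rather than established. Under the assumed mechanisms at 30% loss, selection in one arm moves the contrast by about 0.1–0.3, below the completers' standard error of √0.190 = 0.44 but up to about a fifth of the assumed effect. At 42% loss the second simulation gives somewhat larger shifts (one-arm estimates of 0.98–1.12 or 1.54–1.68).

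The precision gain is modest for a plain model and larger with a common baseline, and comes mostly from baseline data. The gap in the text and the baseline-only gain do not need the Tanner IV visit; the additional 2 to 7 points do. The sizes rest on SD 1.85, correlation 0.5 over two years, 36 completers, the assumed Tanner IV correlations and the assumed dropout rules. The common-baseline figures apply to the randomised obese arms only, not to the comparison with lean controls.

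**What to change.** 1. Reconcile the visit schedule: the Specific Aim 1 Approach and its tables against Section A and the Specific Aim 2 Approach. State which IVGTTs each group has, and correct the dropout arithmetic (30% or 42%).
2. Make the main analysis a likelihood-based repeated-measures model on all participants with a baseline IVGTT, grouped as randomised or recruited. Use every IVGTT visit actually scheduled, group by visit, and unstructured covariance. Give the two randomised obese arms a common baseline mean and the lean controls a separate one. Estimate the Tanner V and six-month post-treatment contrasts from this model.
3. Adjust only for baseline covariates: sex, the stratification factors, and baseline adiposity where appropriate. Move the models with 2-year change in percent body fat and BMI to secondary analyses. If those covariates stay in the main model, they drop the same participants again.
4. Keep the completers' regression as a sensitivity analysis and add one for informative dropout.

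The cost is analysis text plus the schedule reconciliation; no new data are needed, and SAS, already named, fits the model. The downside is that the model assumes dropout is explained by observed data, hence the last sensitivity analysis. If no Tanner IV IVGTT is kept, lean dropouts contribute only their baselines, so the gain for the lean–obese contrast is small.
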